
- s. HBVDNA testing will be performed at Weeks 12, 24, 34, 48, and Early Termination for subjects who were enrolled with a positive HBcAb and a negative HBVDNA in those regions for which Hep B prevalence has been reported at a rate of >5.0% or if required by local standard of care (refer to [Section 7.5.11](#) for information regarding which screening laboratory results should be used to determine whether HBVDNA testing should be performed). Testing at additional time points may be performed as per the local standard of care. For Japan-specific requirements see [Appendix 5.1](#). For all other countries, please refer to [Appendix 2](#) for testing algorithm, reflex testing, and full eligibility criteria.
- t. Varicella-zoster virus immunoglobulin G antibody (VZV IgG Ab) testing is required to confirm eligibility only in adolescent subjects who have no documented evidence of having received varicella vaccination (2 doses).
- u. A serum sample will be collected at baseline and submitted to the central lab. The sample will be stored and analyzed at a later date only at the sponsor's request. For example, in certain cases of suspected viral infection (eg, disseminated herpes zoster or varicella), the sponsor may request to analyze the sample to determine if the subject had exposure to that virus.
- v. A documented TB test performed within 12 weeks prior to Day 1 is acceptable. Subjects with a history of tuberculosis may not require TB testing as per the protocol exclusion criteria in [Section 4.2 Exclusion Criterion 21](#). Perform TB test procedure using the QuantiFERON®-TB Gold In Tube (QFT-G) test. If QFT-G test is not available, the T-SPOT®.TB (T-Spot) test can be used. A negative Purified Protein Derivative (PPD) test can be substituted for the QFT-G test or T-Spot test only under specific circumstances described in [Section 7.5.8](#).
- w. Dosing instructions will be provided to the subject and reviewed by the site at each visit. Subjects should be encouraged to take the medication in the morning whenever possible. Subjects should take the medication at approximately the same time every day. However, at study visit days, subjects are to be instructed to refrain from dosing at home and are to take the dose in the clinic.

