**Table 2. Number and Type of Tablets for Each Treatment Sequence**

Treatment Sequence	Loading Period Day 1 to Week 4 (No. of Tablets)	Maintenance Period Weeks 4 to 24 (No. of Tablets)	First 4 Weeks of Extension Period Weeks 24 to 28 (No. of Tablets)	Remainder of Extension Period Weeks 28 to 48 (No. of Tablets)
A	4 of 50 mg active 3 of 10 mg size pbo	1 of 50 mg active 3 of 10 mg size pbo	1 of 50 mg active 3 of 50 mg size pbo 3 of 10 mg size pbo	1 of 50 mg active 3 of 10 mg size pbo
B	4 of 50 mg active 3 of 10 mg size pbo	1 of 50 mg size pbo 3 of 10 mg active	4 of 50 mg size pbo 3 of 10 mg active	1 of 50 mg size pbo 3 of 10 mg active
C	1 of 50 mg active 3 of 50 mg size pbo 3 of 10 mg size pbo	1 of 50 mg active 3 of 10 mg size pbo	1 of 50 mg active 3 of 50 mg size pbo 3 of 10 mg size pbo	1 of 50 mg active 3 of 10 mg size pbo
D	4 of 50 mg size pbo 3 of 10 mg active	1 of 50 mg size pbo 3 of 10 mg active	4 of 50 mg size pbo 3 of 10 mg active	1 of 50 mg size pbo 3 of 10 mg active
E	4 of 50 mg size pbo 1 of 10 mg active 2 of 10 mg size pbo	1 of 50 mg size pbo 1 of 10 mg active 2 of 10 mg size pbo	4 of 50 mg size pbo 1 of 10 mg active 2 of 10 mg size pbo	1 of 50 mg size pbo 1 of 10 mg active 2 of 10 mg size pbo
F	4 of 50 mg size pbo 3 of 10 mg size pbo	1 of 50 mg size pbo 3 of 10 mg size pbo	4 of 50 mg active 3 of 10 mg size pbo	1 of 50 mg active 3 of 10 mg size pbo

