#### **6.2.7. Visit 8, Day 169/Week 24 ( $\pm 7$ days)**

The following procedures will be completed:

- Administer PRO questionnaires: AAPPO, PGI-C, P-Sat, HADS, SF36v2 Acute, AARU, WPAI: AA in adults, and EQ-5D-5L in adults or EQ-5D-Y in adolescents.
- Obtain vital signs: pulse rate, blood pressure, respiratory rate (after at least 5 minutes of rest), and temperature.
- Perform single 12-lead ECG.
- Obtain height and weight.
- Conduct complete physical examination.

- Perform audiological evaluation.
- Obtain fasting samples for fasting lipid panel.
- Obtain samples for laboratory testing: hematology, blood chemistry, urinalysis, HBVDNA (if applicable), IP-10, FACS-TBNK, and immunoglobulins (IgA, IgG, IgM).
- Obtain Prep B1, B2, and R1 samples.
- Confirm whether menarche has started in previously premenarchal subjects. If menarche has started, the subject must undergo a pregnancy test and establish willingness and ability to comply with contraception requirements (see [Section 4.3](#)) going forward in study.
- Perform urine pregnancy test (female subjects of childbearing potential only).
- Confirm proper contraception is being used.
- Capture photographs.
- Conduct clinical evaluations: SALT, EBA, ELA, assessment of fingernails affected by AA, and CGI-AA.
- Conduct C-SSRS.
- Review any changes in the subject's concomitant treatments information.
- Assess for occurrence of AEs.
- Collect study drug from subject, administer dose to subject, and perform accountability procedures.
- Provide and review dosing instruction.
- Dispense new study drug to the subject.

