#### **6.2.8. Visit 9, Day 183/Week 26 ( $\pm 3$ days)**

The following procedures will be completed:

- Perform urine pregnancy test (female subjects of childbearing potential only).
- Obtain samples for other laboratory testing: hematology.
- Confirm whether menarche has started in previously premenarchal subjects. If menarche has started, the subject must undergo a pregnancy test and establish

willingness and ability to comply with contraception requirements (see [Section 4.3](#)) going forward in study.

- Confirm proper contraception is being used.
- Review any changes in the subject's concomitant treatments information.
- Assess for occurrence of AEs.
- Collect study drug from subject, administer dose to subject, and perform accountability procedures.
- Provide and review dosing instruction.
- Dispense new study drug to the subject.

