9. APPENDICES

9.1. Definition and Use of Visit Windows in Reporting

Visit windows will be used for efficacy and PRO variables, and for any safety data that display or summarize by study visit.

Table 6. Visit Windows

Visit Label	Target Day	Definition
Baseline	1	<=Day 1
Week 2	15	Days 2 to 21
Week 4	29	Days 22 to 42
Week 8	57	Days 43 to 70
Week 12	85	Days 71 to 105
Week 18	127	Days 106 to 147
Week 24	169	Day 148 to 179 and <=EDay ^a 1
Week 26	183	Days 180 to 189 and >EDay 1
Week 28	197	Days 190 to 217 and >EDay 1
Week 34	239	Days 218 to 259 and >EDay 1
Week 40	281	Days 260 to 308 and >EDay 1
Week 48	337	≥Day 309 and >EDay 1

- a. EDay =relative day of the first dose date in the extension phase based on dosing log data after week 24 visit. If Week 24 dose log is missing, earliest dosing date from Week 26 and onward will be considered start of Extension.

The Baseline value is defined in [Section 3.3](#).

Some endpoints were not scheduled to be assessed at each visit. In this case, the unscheduled ‘windowed’ visit will be moved to the next scheduled windowed visit for analysis and reporting. For example, HADS were not to be assessed at Week 18, Week 28, Week 34 and Week 40, if data falls under Week 18 it will be treated as Week 24; and data that falls under Weeks 28, 34, 40 will be treated as Week 48.

If more than one observation falls within a visit window, the observation that is the closest to the targeted day will be used for the summary tables. If two visits are equally distant from the target day, the data from the later visit will be used.

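### When the Week 24 dose log is missing, the fallback extension start in SAP Table 6 is about two weeks late, so Week 26 hematology can lose its visit label and some on-drug values can be labelled Week 24

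*SAP*

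**What the plan says.** SAP 9.1 applies the Table 6 windows to efficacy and PRO variables and to safety data shown by visit. Around the switch to extension treatment, a row needs both a day range and a position relative to EDay 1:

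- Week 24: "Day 148 to 179 and <=EDay" 1.
- Week 26: "Days 180 to 189 and >EDay 1".

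Footnote a gives the normal definition: "EDay =relative day of the first dose date in the extension phase based on dosing log data after week 24 visit". It then gives the fallback: "If Week 24 dose log is missing, earliest dosing date from Week 26 and onward will be considered start of Extension".

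The protocol places the start of the extension at Week 24:

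- Table 2 heads the third dosing column "First 4 Weeks of Extension Period Weeks 24 to 28". In that column sequences F and G change from placebo to active tablets.
- Section 6.2.7 (Week 24 visit) includes "Dispense new study drug to the subject".
- Section 6.2.8 (Week 26 visit) includes "Obtain samples for other laboratory testing: hematology", and a dose is given at the same visit.
- Note w of the Schedule of Activities says that on visit days "subjects are to be instructed to refrain from dosing at home and are to take the dose in the clinic".

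SAP 5.2 pools F and G as placebo for comparisons up to Week 24. It keeps all seven sequences apart for summaries to Week 48.

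**The concern.** For subjects in F and G, EDay 1 decides whether a value counts as placebo or active. If one log is missing, the fallback moves that boundary from the Week 24 visit to the Week 26 visit or later. The same record is then classified differently according to whether a log was returned.

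Two things are at stake. First, Week 26 is the only scheduled blood count between Weeks 24 and 28, the four weeks in which Table 2 gives sequence F four 50 mg active tablets a day. Protocol 1.4.1 reports mean falls of 18% in platelets and 24% in lymphocytes during the 200 mg induction of the Phase 2a study, so a by-visit hematology table has a reason to show this visit. Second, a value taken on active drug could appear under Week 24 in the pooled placebo group.

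**Working it through.** **Inputs.** Table 6 rows and footnote a (SAP 9.1). Allowed visit days (Schedule of Activities; protocol Appendix 6.3, Table 8): Week 24 = 169 ± 7 = Days 162–176; Week 26 = 183 ± 3 = Days 180–186. That makes 15 × 7 = 105 combinations.

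**Table 6 with a known start date.** Target days are 7 × week + 1, giving 169, 183 and 197 for Weeks 24, 26 and 28, as in the table. With EDay 1 on the Week 24 visit day, the Week 26 draw is labelled Week 26 in 105 of 105 combinations.

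**Delay under the fallback.** Taking EDay 1 as the Week 26 visit day:

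- nominal: 183 − 169 = 14 days;
- shortest: 180 − 176 = 4 days;
- longest: 186 − 162 = 24 days.

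The count runs from dispensing at the Week 24 visit. The nominal 14 days is half of the 28-day period from Week 24 to Week 28.

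**Week 26 hematology.** Let the draw be on day d, with d from 180 to 186. The dose is taken at the same visit, so EDay 1 = d.

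- Week 26 row: needs d > EDay 1, that is d > d. Fails.
- Week 24 row: needs d ≤ 179. Fails.

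The draw has no label on 7 of 7 allowed days. The result is the same if the first logged dose is the next day. The SAP 9.1 rule that carries data forward to the next scheduled visit applies to a value that falls in a window where the endpoint was not scheduled. This value falls in no window, so that rule does not recover it. The loss depends only on EDay 1, so it can occur in all seven sequences.

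If the Week 26 log is missing as well and EDay 1 becomes Day 197, observations on Days 183 and 197 are both unlabelled. That needs two missing logs.

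**On-drug values labelled Week 24.** Take the nominal case. With EDay 1 = 169, no day from 170 to 179 is labelled Week 24. With the fallback EDay 1 = 183, all ten are.

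Whether such a value is used depends on the tie-break in SAP 9.1: closest to Day 169, and the later one if equal. A value on day d after a Week 24 visit on day v replaces the visit value when d − 169 ≤ 169 − v, that is d ≤ 338 − v, and this needs v < 169.

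- v = 162: days 163 to 176 can replace it, for example a re-test on Day 169.
- v = 168: only Days 169 and 170 can.
- v ≥ 169: every later day is farther away, so nothing is replaced.

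If there is no visit value, a late one up to Day 179 fills the Week 24 slot. Protocol Appendix 3.1 requires re-tests within a week for certain blood results. Appendix 6 has procedures missed because of COVID-19 done at the next opportunity, even outside the window, and allows drug to be shipped to the subject.

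**Number of subjects.** The documents give no rate of missing Week 24 logs. Randomisation 2:2:2:2:1:1:1 of 660 gives 660 / 11 = 60 each in F and G, 120 together. For an assumed 2% to 10%:

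| Group | Subjects | 2% | 10% |
|---|---|---|---|
| All sequences | 660 | 13 | 66 |
| F and G | 120 | 2 | 12 |
| F only | 60 | 1 | 6 |

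These are the subjects to whom the fallback would apply. Fewer would also have a repeat or late value before Day 180.

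**The case against.** The strongest objection is that the footnote does not define the Week 24 dose log, or say whether Week 26 refers to the dates of doses or to records collected at that visit. At Week 26 the site accounts for the supply given at Week 24, and under Appendix 6 logs are reviewed for intake since the last contact. A record collected then could hold dates from the first extension dose. EDay 1 would be about Day 169 or 170, and a Day 183 draw would keep its label. An EDay 1 of Day 180 would also label a Day 183 draw Week 26. This stands in part: a label loss in every affected subject cannot be claimed. But the footnote speaks of the earliest dosing date from Week 26 onward, which most naturally means dates of doses, and the ambiguity is itself a reason to reword.

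A second objection is that little depends on the label. This largely stands. The blood count stays in the database. The safety rules in protocol Appendix 3 act on actual results. Neither the laboratory-abnormality incidence (SAP 6.7.2, 9.3) nor the adverse-event periods (SAP 6.7.1) are stated to use EDay. A reader might infer that the Week 26 count is removed from the safety evaluation; the documents support only its loss from by-visit summaries.

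Third, replacing a Week 24 value by a re-test needs a missing log, a Week 24 visit before Day 169 and a re-test in a limited range of days. That stands. It does not cover a late first assessment, which needs no early visit.

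**Conclusion.** On its natural reading, the fallback contradicts the protocol's extension start at Week 24. It sets EDay 1 nominally 14 days late (4 to 24 over the allowed days), leaves Week 26 hematology without a label, and lets on-drug values up to Day 179 count as Week 24 in F and G.

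A reader might go further and infer that the primary or key secondary results are compromised. The documents do not support that. A Week 24 SALT or PGI-C taken on or before the first extension dose keeps its label, and neither is scheduled at Week 26. Only an assessment made after the switch and by Day 179, in a subject whose log is also missing, could be counted wrongly, and nothing shows how often that would occur.

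The conclusion assumes that the missing log is the one holding the first extension doses, that no earlier extension dose date is available, and that visits fall within their windows. The frequency is unknown and probably small; the 2% to 10% above is only illustrative. Severity: minor.

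**What to change.** Replace the fallback sentence in footnote a with wording such as:

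*When the Week 24 dose log is missing, EDay 1 is the earliest recorded extension dose date in any log that covers the period from the Week 24 visit. If none is recorded before the Week 26 visit, EDay 1 is the Week 24 visit date (for a remote visit, the IRT dispensing date, or the date of receipt if it is in the database).*

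This settles which log is meant. Where the visit date is used, the Week 26 draw is labelled Week 26 in 105 of 105 visit-day combinations, and no active-drug day in F or G precedes EDay 1.

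The cost is one sentence in the SAP, to be settled before unblinding. Visit and IRT dates should already be held. The receipt date is optional because protocol Appendix 6.4 places shipment tracking in site source records. The downside is that the proxy may be slightly earlier than the true first extension dose if the start was delayed, for example while drug was withheld pending laboratory samples.

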#### **6.3.2. Early Termination Visit**

For subjects who discontinue early from the study, the procedures scheduled for early termination (ET) Visit will be performed on the last day the subject takes the investigational product or as soon as possible thereafter. Subject will then require a Follow-up visit occurring within 28 (+7 days).

The following procedures will be completed:

- Administer PRO questionnaires: AAPPO, PGI-C, P-Sat, HADS, SF36v2 Acute, AARU, WPAI: AA in adults, and EQ-5D-5L in adults or EQ-5D-Y in adolescents.
- Obtain vital signs: pulse rate, blood pressure, respiratory rate (after at least 5 minutes of rest), and temperature.

- Perform single 12-lead ECG.
- Obtain height and weight.
- Conduct complete physical examination.
- Perform audiological evaluation.
- Obtain fasting samples for fasting lipid panel.
- Obtain samples for laboratory testing: hematology, blood chemistry, urinalysis, HBVDNA (if applicable), FACS-TBNK, and immunoglobulins (IgA, IgG, IgM).
- Confirm whether menarche has started in previously premenarchal subjects. If menarche has started, the subject must undergo a pregnancy test and establish willingness and ability to comply with contraception requirements (see [Section 4.3](#)) through 28 days after the last dose of study medication.
- Perform urine pregnancy test (female subjects of childbearing potential only).
- Confirm proper contraception is being used.
- Capture photographs.
- Conduct clinical evaluations: SALT, EBA, ELA, assessment of fingernails affected by AA, and CGI-AA.
- Conduct C-SSRS.
- Review any changes in the subject's concomitant treatments information.
- Assess for occurrence of AEs.
- Collect study drug from subject and perform accountability procedures.

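### SAP 9.1 moves off-schedule values forward to the next scheduled visit with no distance limit, so dropouts' HADS scores can enter the tested Week 24 analysis up to 9 weeks early and the untested Week 48 estimates 21 weeks early or more

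*SAP*

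**What the plan says.** SAP 9.1 applies visit windows to efficacy and PRO variables and to safety data shown by visit. For an endpoint not scheduled at every visit, it says that "the unscheduled ‘windowed’ visit will be moved to the next scheduled windowed visit for analysis and reporting". HADS is the worked example. For the placebo-controlled period the instruction is "if data falls under Week 18 it will be treated as Week 24". For the extension phase it reads "data that falls under Weeks 28, 34, 40 will be treated as Week 48". The Week 18 window is "Days 106 to 147", the Week 26 window "Days 180 to 189 and >EDay 1" and the Week 28 window "Days 190 to 217 and >EDay 1". If several values share a window, the one nearest the target day is used. The section sets no limit on how far a value may move and does not mention early termination.

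Protocol 6.3.2 places the early-termination visit on the final dosing day or soon after. Its procedures begin "Administer PRO questionnaires: AAPPO, PGI-C, P-Sat, HADS, SF36v2 Acute" and also include weight, audiology and immunoglobulins.

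SAP 5.3.2 does not impute missing post-baseline values of longitudinal continuous endpoints and relies on a repeated-measures model under missing at random. SAP 6.3.8 and 6.3.9 use that model for change in HADS. SAP 6.3.10 and 6.3.11 use observed cases for HADS improvement. All four HADS endpoints are secondary for the EMA (SAP Table 4).

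**The concern.** An early-termination visit can fall in any window. A subject who stays on study has a true Week 24 or Week 48 value near the target day, and that value wins. A subject who left has none, so the early-termination value takes the later visit's place. The rule therefore acts mainly on dropouts.

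Three things follow:
- A score that describes one point in time is analysed as if it described a later one. HADS asks about the past week (Protocol 7.8.4), so a Day 190 score carries no direct information on Day 337.
- The MMRM receives an apparently observed Week 24 or Week 48 value where SAP 5.3.2 would leave that visit missing and let the model deal with it. The observed-case HADS summaries include subjects who were not observed then.
- The label overstates exposure. Sequences F and G start active drug at Week 24 (Protocol Table 2). If the extension starts near Day 169, a Day 190 value reflects about 190 − 169 = 21 days of active drug but is shown as Week 48.

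**Working it through.** **Inputs.** Windows and target days are from SAP Table 6: Week 24 target Day 169, window from Day 148; Week 48 target Day 337, window from Day 309. HADS is scheduled at Weeks 4, 8, 12, 24 and 48 (SAP 6.3.8 to 6.3.11). After baseline, weight is scheduled and summarised at Weeks 24 and 48 only (Schedule of Activities; SAP 6.7.3).

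**Reproducing the plan's example.** Sending each off-schedule window to the next scheduled HADS visit gives Week 18 to Week 24, and Weeks 28, 34 and 40 to Week 48, as SAP 9.1 states. The general sentence also sends Week 26 to Week 48, which the example omits.

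**Largest shift** = target day of the destination visit − first day of the source window.

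| Measure | Source window opens | Labelled as | Shift |
|---|---|---|---|
| HADS | Week 18, Day 106 | Week 24 | 169 − 106 = 63 days (9.0 weeks) |
| HADS | Week 26, Day 180 | Week 48 | 337 − 180 = 157 days (22.4 weeks) |
| HADS | Week 28, Day 190 | Week 48 | 337 − 190 = 147 days (21.0 weeks) |
| HADS | Week 34, Day 218 | Week 48 | 337 − 218 = 119 days (17.0 weeks) |
| HADS | Week 40, Day 260 | Week 48 | 337 − 260 = 77 days (11.0 weeks) |
| Weight | Week 2, Day 2 | Week 24 | 169 − 2 = 167 days (23.9 weeks) |

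These are maxima. At the end of the Week 18 window the HADS shift is 169 − 147 = 22 days.

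**Comparison.** Inside a visit's own window, a value can precede the target by at most 169 − 148 = 21 days at Week 24 and 337 − 309 = 28 days at Week 48.

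**Endpoints not moved into Week 24.** SALT and PGI-C are both scheduled at Week 18, so a value from that window stays at Week 18.

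**How many subjects.** The documents give no dropout rate, so one is assumed, spread evenly over Days 1 to 169, with every dropout attending the termination visit. Only Days 106 to 147 feed HADS into Week 24, which is 147 − 106 + 1 = 42 days. Share relabelled = 42/169 × dropout:
- 5% dropout: 1.2%
- 10% dropout: 2.5%
- 20% dropout: 5.0%

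In a group of 120, 10% dropout gives about 120 × 0.025 = 3 subjects. The share is smaller if some dropouts have no termination visit.

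**The case against.** The best defence is that this is an openly stated visit-assignment rule, with an example, applied to values that were actually observed. SAP 5.3.2 bars imputing missing values, and nothing is imputed here. A reader might call the rule last observation carried forward under another name. The documents do not support that: each value is assigned once, and a Day 106 score goes to Week 24 and not also to Week 48. What remains is mis-timing that fills visits the model was meant to treat as missing.

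The reach is also limited, and that stands. The longest HADS shifts affect Week 48 only, where SAP 6 and 5.2.3 give estimates without tests and the Week 48 MMRM covers only the initially active groups. The former-placebo example can therefore appear only in descriptive tables. The tested HADS analysis ends at Week 24, where the shift is at most 63 days, and HADS is exploratory outside the EMA analysis. Actual days of dosing are summarised separately (SAP 6.6.3).

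A reader might extend the 167-day figure to audiology, ECG, immunoglobulins or lymphocyte subsets. ECG and lymphocyte subsets have a Week 4 visit, so it cannot apply to them. SAP 6.7.6 does not say that audiology is summarised by visit, and the documents do not settle whether the windows cover immunoglobulins. Weight is the clear case.

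Finally, dropping these values has a cost: the model loses a dropout's last score, which may make missing at random less plausible.

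**Conclusion.** The point holds at moderate weight. SAP 9.1 states a rule that puts mis-timed values, mainly from dropouts, into by-visit results. The day counts follow directly from Table 6. The share affected at Week 24, about 2.5% of subjects with a range of about 1% to 5%, rests on assumed dropout of 10% (5% to 20%), even timing up to Day 169 and full attendance at the termination visit. A reader might suppose that every early terminator is relabelled; for HADS, those whose value falls in the Week 4, 8, 12, 24 or 48 window are not.

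The finding gives no reason to doubt the primary or key secondary results at Week 24. What it affects is the HADS analysis for the EMA, other sparsely scheduled measures, and the meaning of the Week 24 and Week 48 labels.

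**What to change.** Delete the relabelling sentence and its HADS example from SAP 9.1, and state that a by-visit analysis uses only values inside that visit's own Table 6 window. List off-schedule early-termination values, keep them in safety summaries that are not by visit, and let the MMRM handle the missing visit.

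A distance limit in place of deletion would add little. A 21-day limit would admit values from Day 169 − 21 = 148 for Week 24 and Day 337 − 21 = 316 for Week 48, and both days already lie inside the existing windows.

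The cost is a short SAP edit before database lock. A few dropouts' last values leave the by-visit tables and the MMRM. If the team wants to see whether that matters, the present rule can be kept as a sensitivity analysis for HADS.
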